5.3.3 Dose Modifications

5.3.3.1 Pembrolizumab Dose Modification and Toxicity Management for Immune-Related AEs Associated with Pembrolizumab and Combination Therapy

AEs associated with pembrolizumab exposure, including coadministration with additional compounds, may represent an immunologic etiology. These immune-related AEs (irAEs) may occur shortly after the first dose or several months after the last dose of pembrolizumab/combination treatment and may affect more than one body system simultaneously. Therefore, early recognition and initiation of treatment is critical to reduce complications. Based on existing clinical study data, most irAEs were reversible and could be managed with interruptions of pembrolizumab/combination treatment, administration of corticosteroids and/or other supportive care. For suspected irAEs, ensure adequate evaluation to confirm etiology or exclude other causes. Additional procedures or tests such as bronchoscopy, endoscopy, skin biopsy may be included as part of the evaluation. Dose modification and toxicity management guidelines for irAEs associated with pembrolizumab/combination treatment are provided in Table 5.. See Section 5.9 for supportive care guidelines, including use of corticosteroids.

Attribution of Toxicity:

When study interventions are administered in combination, attribution of an adverse event to a single component is likely to be difficult. Therefore, while the investigator may attribute a toxicity event [to the combination, to [trebananib alone] or to pembrolizumab alone], for adverse events listed in Table 5, both interventions must be held according to the criteria in Table 5 Dose Modification and Toxicity Management Guidelines for Immune-Related Adverse Events Associated with Pembrolizumab.

Holding Study Interventions:

When study interventions are administered in combination, if the AE is considered immune-related, both interventions should be held according to the recommended dose modifications.

Restarting Study Interventions:

Participants may not have any dose modifications (no change in dose or schedule) of pembrolizumab in this study, as described in Table 5.

- If the toxicity does not resolve or the criteria for resuming treatment are not met, the participant must be discontinued from all study interventions
- If the toxicities do not resolve and conditions are aligned with what is defined in Table 5, the combination of trebananib and pembrolizumab may be restarted at the discretion of the

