
investigator. [In these cases where the toxicity is attributed to the combination of trebananib and pembrolizumab or trebananib alone, re-initiation of pembrolizumab as a monotherapy may be considered at the principal investigator's discretion.]

Table 5 Dose modification and toxicity management guidelines for immune-related AEs associated with pembrolizumab monotherapy and IO combinations

General instructions:

1. Severe and life-threatening irAEs should be treated with IV corticosteroids followed by oral steroids. Other immunosuppressive treatment should begin if the irAEs are not controlled by corticosteroids.
2. Study intervention must be permanently discontinued if the irAE does not resolve or the corticosteroid dose is not ≤ 10 mg/day within 12 weeks of the last study intervention treatment.
3. The corticosteroid taper should begin when the irAE is \leq Grade 1 and continue at least 4 weeks.
4. If study intervention has been withheld, study intervention may resume after the irAE decreased to \leq Grade 1 after corticosteroid taper.

irAEs	Toxicity Grade (CTCAE v5.0)	Action With Pembrolizumab	Corticosteroid and/or Other Therapies	Monitoring and Follow-up
Pneumonitis	Grade 2	Withhold	
 • Administer corticosteroids (initial dose of 1 to 2 mg/kg prednisone or equivalent) followed by taper • Add prophylactic antibiotics for opportunistic infections 	
 • Monitor participants for signs and symptoms of pneumonitis • Evaluate participants with suspected pneumonitis with radiographic imaging and initiate corticosteroid treatment
	Recurrent Grade 2, Grade 3 or 4	Permanently discontinue		
Diarrhea/Colitis	Grade 2 or 3	Withhold	
 • Administer corticosteroids (initial dose of 1 to 2 mg/kg prednisone or equivalent) followed by taper 	
 • Monitor participants for signs and symptoms of enterocolitis (ie, diarrhea, abdominal pain, blood or mucus in stool with or without fever) and of bowel perforation (ie, peritoneal signs and ileus) • Participants with \geq Grade 2 diarrhea suspecting colitis should consider GI consultation and performing endoscopy to rule out colitis
	Recurrent Grade 3 or Grade 4	Permanently discontinue		

irAEs	Toxicity Grade (CTCAE v5.0)	Action With Pembrolizumab	Corticosteroid and/or Other Therapies	Monitoring and Follow-up

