^b	AST/ALT: >5.0 to 20.0 x ULN, if baseline normal; >5.0 to 20.0 x baseline, if baseline abnormal; bilirubin: >3.0 to 10.0 x ULN if baseline normal; >3.0 to 10.0 x baseline if baseline abnormal			
^c	AST/ALT: >20.0 x ULN, if baseline normal; >20.0 x baseline, if baseline abnormal; bilirubin: >10.0 x ULN if baseline normal; >10.0 x baseline if baseline abnormal			
^d	The decision to withhold or permanently discontinue pembrolizumab is at the discretion of the investigator or treating physician. If control achieved or ≤ Grade 2, pembrolizumab may be resumed.			
^e	Events that require discontinuation include, but are not limited to: encephalitis and other clinically important irAEs (eg, vasculitis and sclerosing cholangitis).			

Dose modification and toxicity management of infusion-reactions related to pembrolizumab

Pembrolizumab may cause severe or life-threatening infusion-reactions including severe hypersensitivity or anaphylaxis. Signs and symptoms usually develop during or shortly after drug infusion and generally resolve completely within 24 hours of completion of infusion. Dose modification and toxicity management guidelines on pembrolizumab associated infusion reaction are provided in Table 6.

Table 6. Pembrolizumab Infusion Reaction Dose Modification and Treatment Guidelines

NCI CTCAE Grade	Treatment	Premedication at subsequent dosing
Grade 1 Mild reaction; infusion interruption not indicated; intervention not indicated	Increase monitoring of vital signs as medically indicated until the participant is deemed medically stable in the opinion of the investigator.	None

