- Noncompliance with trial treatment or procedure requirements
- The participant is lost to follow up.
- The participant completes 24 months of uninterrupted treatment with pembrolizumab or 35 administrations of study pembrolizumab, whichever is later
- Administrative reasons
- Unacceptable adverse event(s), including:
 - Any Grade 2 drug-related uveitis or eye pain or blurred vision that does not respond to topical therapy and does not improve to Grade 1 severity within the re-treatment period OR requires systemic treatment
 - Grade 3 drug-related autoimmune or inflammatory event including uveitis, pneumonitis, diarrhea, colitis, neurologic adverse events, hypersensitivity reaction, or infusion reaction of any duration requires discontinuation.
 - Any Grade 3 or 4 drug-related laboratory imbalance or electrolyte abnormality, not associated with underlying organ pathology and that do not require treatment except for electrolyte replacements do not require treatment discontinuation, with the following exceptions with approval of the Principal Investigator:
 - Hypophysitis or pan-hypopituitarism any grade should discontinue treatment.
 - Grade 4 amylase or lipase abnormalities that are not associated with DM, associated liver or gall bladder inflammation clinical manifestations of pancreatitis may stay on study.
 - Any drug-related liver function test (LFT) abnormality that meets the following criteria requires discontinuation: Grade 4 AST or ALT.

- Grade 3 drug-related thrombocytopenia >7 days or associated with bleeding requires discontinuation.
- For patients with skin-only toxicity, when symptoms improve to Grade 1 or less, steroid taper should be started and continued over no less than 4 weeks. Discontinue pembrolizumab if unable to reduce corticosteroid dose for irAEs to ≤ 10 mg. Pembrolizumab treatment may be restarted and the dose modified as specified in the protocol.
- Patients with endocrinopathy (e.g. thyroiditis, hypophysitis) and no other autoimmune/inflammatory event may be restarted after a short course of steroids and/or on a stable replacement regimen.
- Any dosing interruption lasting >12 weeks with the following exceptions:
 - Dosing interruptions >12 weeks that occur for non-drug-related reasons may be allowed if approved by the Principal Investigator. Prior to re-initiating treatment in a participant with a dosing interruption lasting >12 weeks, the Principal Investigator must be consulted.

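### Section 5.3.3.1 gives two opposite restart instructions for an unresolved immune-related event that meets Table 5 conditions; in practice this mainly affects controlled endocrine events

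*Combined protocol and SAP*

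**What the plan says.** Section 5.3.3.1 requires both drugs to be held for the events in Table 5. Two bullets on restarting follow.

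- Bullet 1: "If the toxicity does not resolve or the criteria for resuming treatment are not met, the participant must be discontinued from all study interventions".
- Bullet 2, which leaves the choice to the investigator: where "toxicities do not resolve and conditions are aligned with what is defined in Table 5, the combination of trebananib and pembrolizumab may be restarted".

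These provisions bear on the same decision:

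- **Table 5, general instruction 2:** "Study intervention must be permanently discontinued if the irAE does not resolve or the corticosteroid dose is not" down to 10 mg/day or less within 12 weeks of the last treatment.
- **Table 5, general instruction 3:** the steroid taper starts at or below "Grade 1 and continue at least 4 weeks".
- **Table 5, general instruction 4:** "If study intervention has been withheld, study intervention may resume after the irAE decreased to" Grade 1 or lower after the taper.
- **Table 5, footnote d** (T1DM/hyperglycemia, Grade 3-4 hypophysitis, Grade 3-4 hyperthyroidism): "The decision to withhold or permanently discontinue pembrolizumab is at the discretion of the investigator or treating physician", and "If control achieved or ≤ Grade 2, pembrolizumab may be resumed".
- **Section 5.3.3.2:** trebananib ends once more than three doses have to be held.
- **Section 5.4:** endocrinopathies controlled on physiologic hormone replacement alone may resume. Adrenal insufficiency and hypophysitis are excluded. The lead-in to this list refers to non-autoimmune events, so its scope is unclear.
- **Section 5.12:** "Patients with endocrinopathy (e.g. thyroiditis, hypophysitis) and no other autoimmune/inflammatory event may be restarted" after a short steroid course or on stable replacement. The same section also says that hypophysitis of any grade should lead to discontinuation.

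**The concern.** A restart rule has to give one answer for each patient. Here the same finding, toxicity that has not resolved, leads to a mandatory stop under one bullet and a permitted restart under the next. The ordinary case, a toxicity that resolves with Table 5 satisfied, appears in neither bullet.

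Safety and tolerability are the primary objectives, and these bullets govern whether a patient is re-exposed or permanently taken off drug. Take a patient with new-onset T1DM controlled on insulin. One site could follow bullet 1 and stop both drugs. Another could follow bullet 2 with footnote d and restart. Both would be complying with the protocol. The discretion in footnote d is intended; a mandatory stop that contradicts it is not. Such differences would also enter the disposition and treatment summaries of Sections 14.3 and 14.4.

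**Working it through.** The plan states no figure on this point, so the check is mainly one of logic.

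**Step 1: the two bullets.** Let R mean that the toxicity has resolved and T that the Table 5 conditions for resuming are met.

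| Case | Bullet 1 | Bullet 2 as written | Bullet 2 without *not* |
|---|---|---|---|
| R and T | silent | silent | may restart |
| R, not T | stop | silent | silent |
| not R, T | stop | may restart | silent |
| not R, not T | stop | silent | silent |

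As written, the third row has two opposite answers and the first row has none. Without *not*, every row has exactly one answer, and the first row agrees with instruction 4. That is the basis for inferring a stray word.

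**Step 2: which events can fall in the third row.** For most irAEs, instruction 4 makes T depend on improvement to Grade 1 or lower, and instruction 2 stops drug if the event is unresolved at 12 weeks. If *resolve* means Grade 1 or lower, the row is then essentially empty. If it means complete resolution, residual Grade 1 events also fall in it. For the three footnote d events, control or Grade 2 or lower is enough to resume pembrolizumab, so T can hold without R.

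**Step 3: how far restart of the combination is possible.**

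- Trebananib doses in induction: 3 per cycle (Days 1, 8 and 15) × 4 cycles = 12.
- Shortest steroid taper: 4 weeks × 1 dose per week = 4 doses, before counting any dose missed before the taper began.
- Limit on held doses: 3. Since 4 > 3, trebananib ends.

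This assumes that doses missed during the taper count as held. The assumption is needed because Section 5.3.3.1 also speaks of trebananib being delayed along with pembrolizumab. On this reading, a steroid-treated irAE during induction normally ends trebananib, whatever bullet 2 says.

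Of the three footnote d events, Table 5 lists corticosteroids for one (hypophysitis) and not for the other two (T1DM/hyperglycemia and hyperthyroidism). Combination restart is therefore a real question mainly for those two. For hypophysitis the question is mainly about pembrolizumab alone.

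**Step 4: does deleting *not* suffice?** No. A controlled but unresolved endocrine event would then meet only bullet 1, which stops all drug, against footnote d and Section 5.12 (and Section 5.4 where it applies). Instruction 2, read literally, would stop it as well once 12 weeks had passed.

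**The case against.** The best case for the text is that *not* is deliberate. On that view bullet 2 is the exception for events that are controlled but unresolved, it applies only where Table 5 allows restart, and instruction 4 already handles events that resolve. Part of this stands. Bullet 2 as written does cover the patient with T1DM controlled on insulin, so it would be wrong to infer that bullet 1 simply removes the investigator's discretion. The text gives two answers, not one wrong answer. Nothing marks bullet 2 as an exception, however, and bullet 1 is mandatory.

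A related argument is that the specific footnote overrides the general rule. If so, it overrides both bullet 1 and instruction 2, and most of the endocrine conflict goes away. The protocol states no such order of precedence.

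A shorter repair would be to open bullet 1 with an exception for whatever Table 5 allows. That removes the direct clash, but it leaves instruction 2 untouched and the resolved case missing from the bullets. It would also let bullet 2 restart the combination where footnote d names pembrolizumab only.

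A reader might also infer that bullet 2 opens the way to re-exposure during any unresolved toxicity. The documents do not support that. Bullet 2 is tied to Table 5, and instructions 2 and 4 and the held-dose rule continue to bind.

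**Conclusion.** The contradiction is real and stands in the current text. It is a drafting error in an operative safety rule, with a narrow effect on the management of individual patients. It bites mainly on controlled but unresolved T1DM/hyperglycemia, Grade 3-4 hyperthyroidism and Grade 3-4 hypophysitis. That the cause is a stray *not* is a well-supported inference, not a certainty. The narrowing for trebananib rests on counting doses missed during a taper as held. The documents give no event rate, so no number of patients is claimed.

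It would be wrong to read this as a threat to the trial's results. The RP2D is already fixed, the DLT definition in Section 5.5 does not refer to the restart bullets, and the power statement in Section 14.2 does not depend on them.

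The inconsistency over hypophysitis within Section 5.12 exists whatever the bullets say. It is a separate matter.

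**What to change.** In the next amendment:

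1. Reword bullet 2: *If the toxicities resolve to Grade 1 or lower (after corticosteroid taper where steroids were given) and Table 5 conditions are met, the combination may be restarted at the discretion of the investigator.* Use the same meaning of *resolve* in bullet 1. The words on steroids matter because Table 5 lists none for T1DM/hyperglycemia or hyperthyroidism.
2. Add to both bullet 1 and Table 5 general instruction 2: *except endocrine irAEs that are controlled or Grade 2 or lower, for which pembrolizumab may resume per Table 5 footnote d and Sections 5.4 and 5.12.*
3. State whether trebananib may also restart in those endocrine cases, subject to the held-dose rule in Section 5.3.3.2.

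Separately, the clinical team should settle one rule for hypophysitis across footnote d, Section 5.4 and the two conflicting statements in Section 5.12.

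The cost is one reworded bullet, one exception clause used twice, one sentence on trebananib, and clinical decisions on trebananib restart and hypophysitis. No new data, analysis or patients are needed.

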5.3.3.2 Trebananib Dose Modification and Toxicity Management

Criteria for dose modification as well as specific toxicity management are described below:

For infusion reaction and delayed infusion related reactions: Any potential infusion reaction should be classified based upon severity and time of onset relative to the infusion, and recorded in the case history (and AE eCRF) as an infusion reaction in addition to the underlying symptom.

For infusion reactions occurring within 24 hours of infusion of trebananib and deemed by the investigator to be related to trebananib infusion:

- Mild (grade 1) or moderate (grade 2) – treat per appropriate medical guidelines. Trebananib dosing may resume; however all subsequent doses of trebananib should be administered no faster than over 60 minutes.
- Severe (grade 3) or life-threatening (grade 4) –permanently discontinue trebananib

For infusion – related reactions occurring more than 24 hours after the infusion of trebananib, regardless of whether the reaction is deemed related or not –related to trebananib:

- All grades – treat per appropriate medical guidelines. Contact the Principle Investigator prior to any additional administration of trebananib.

Hemorrhage: Participants who develop any new grade of hemorrhage in the central nervous system will permanently discontinue trebananib.

Participants who develop grade 3 or 4 hemorrhage in any other organ system (pulmonary, GI, etc.) will permanently discontinue trebananib.

Thromboembolic Events: For grade 1 or 2 venous thromboembolic event, no dose modification is required. For grade 3 venous thromboembolic event, or asymptomatic grade 4 venous thromboembolic event (asymptomatic pulmonary embolus), hold trebananib. If the planned duration of the full-dose anticoagulant is ≤ 2 weeks, trebananib should be held until the full-dose anticoagulation period is over. If the planned duration of full-dose anticoagulation is > 2 weeks, trebananib may be resumed during the period of full dose anticoagulation if the following criterion is met:

- The participant must be therapeutically anti-coagulated with an approved anticoagulant agent according to standard prescribing guidelines.

Participants, while on anticoagulation, who develop a second thromboembolic event of grade 2 or higher, should permanently discontinue trebananib.

For symptomatic grade 4 venous thrombosis, permanently discontinue trebananib.

For any grade of arterial thromboembolic event, trebananib will be permanently discontinued.

Edema/lymphedema: A higher incidence of peripheral edema was observed in the trebananib arms vs. the placebo arm in the 20060342 study. To provide a common framework for reporting edema (including lymphedema) investigators should report new edema or edema that significantly worsens from pre-study baseline, and manage their participants as defined in this section.

All adverse events of peripheral edema must be reported and graded as found in this section and NOT per CTCAE v4.0.

Edema of a visceral organ or body cavity, such as pulmonary congestion, ascites, or pleural effusion, should NOT be reported as per this section but per CTCAE v4.0.

Investigators should attempt to ascertain the etiology of edema, which may include, but is not limited to, thromboembolism, chronic corticosteroid dosing, tumor obstruction of lymphatic or blood vessels, congestive heart failure, iatrogenic fluid overload, renal insufficiency, nephrotic syndrome or other significant hypoalbuminemic states.

Edema/lymphedema should be classified as:

- LOCALIZED (confined to a single body area, e.g. lower extremities only) or
- GENERALIZED (contiguous extension to more than a single body area).

Additionally, both localized and generalized edema/lymphedema should be graded as follows:

- Grade 1 (MILD): defined as trace thickening or faint discoloration of the affected area.
- Grade 2 (MODERATE): defined as moderate thickening or marked discoloration; leathery skin texture; papillary formation.
- Grade 3 (SEVERE): defined as severe symptoms that may involve skin blistering or skin breakdown; limitations of activities of daily living (ADL).

The management of edema / lymphedema should be as follows based upon the above grading:

- Grades 1 or 2 – Continue trebananib dosing per protocol and treat edema / lymphedema per appropriate medical and institutional guidelines
- Grade 3 or 4 – Discontinue trebananib permanently. Treat edema /lymphedema per appropriate medical and institutional guidelines

Hypertension: Hypertension (HTN) should be managed per institutional standards and appropriate medical guidelines. trebananib should be held for systolic BP > 200 mmHg or diastolic BP > 110 mmHg, or symptomatic hypertension. trebananib may be resumed at the pre-hold dose upon resolution of symptomatic HTN, systolic BP ≤ 140 mmHg and diastolic BP ≤ 90 mmHg, or returned to participant's baseline blood pressure. If the participant's BP is elevated upon first reading, measurements should be confirmed with a repeat measurement.

For any grade of hypertensive crisis or hypertensive encephalopathy, permanently discontinue trebananib.

Hypokalemia: Participants should have their serum potassium checked as outlined in the Section 9 and managed per institutional guidelines. If hypokalemia is present, replacement should be managed with either oral and/or parenteral replacement, according to institutional practice and to the degree of hypokalemia present. It is recommended that the participant's serum potassium level should be maintained within the normal range, as much as possible, during study treatment. Isolated hypokalemia without clinical sequelae should not be reported as an adverse event.

Pleural Effusion and Ascites: Pleural effusion and ascites should be graded according to CTCAE v4.0. However, since trebananib is known to cause or worsen pre-existing pleural effusions and ascites, these adverse events should be managed as noted below:

Life-threatening pleural effusions or ascites:

- Institute emergency measures per institutional guidelines
- Permanently discontinue trebananib

For all non-life-threatening pleural effusion or ascites:

- Treat per institutional guidelines which may include,

- o non-investigational diuretics,
- o thoracentesis, chest tube drainage or paracentesis
- o pleurodesis
- Investigators should document each paracentesis and /or thoracentesis that occurs while a participant is on study.

Additional toxicities to permanently discontinue trebananib for:

- Gastrointestinal perforation
- Compromised wound healing
- Fistula formation
- Nephrotic syndrome or thrombotic microangiopathy (TMA)
- Reversible posterior leukoencephalopathy syndrome (RPLS)
- Ascites or pleural effusion requiring therapeutic intervention

Trebananib should be temporarily suspended at least 4 weeks prior to an elective surgery. Trebananib should not be resumed until 4 weeks after major surgery, or 2 weeks after minor surgery, and until wounds are healed and drainage tubes removed.

Any grade 1 or 2 toxicities other than those listed above considered to be related to trebananib or the combination of trebananib and pembrolizumab should be managed according to standard medical practice.

When a participant experiences a grade-3 or 4 toxicity other than those listed above considered to be related to trebananib or the combination of trebananib and pembrolizumab, trebananib should be held until the toxicity resolves to \leq grade 1 or the patient's baseline. When resumed trebananib will be dose reduced by one dose level, however, patients at dose level -1 requiring a reduction will discontinue trebananib.

If more than three doses of trebananib need to be held then trebananib will be discontinued.

If a toxicity is assessed as related to trebananib and not pembrolizumab, pembrolizumab may be continued when the toxicity is improved to grade 1 or resolved. If trebananib is to be permanently discontinued, the patient may continue treatment with pembrolizumab alone. If the patient continues pembrolizumab alone due to a toxicity related to trebananib, then they are permitted to skip any Day 8 and Day 15 visits and assessments that coincide with the administration of trebananib.

